### Exclusion Criteria

1. Active infection or wound complication at implant site.
2. Significant psychiatric comorbidity (e.g. uncontrolled depression, psychosis).
3. Planned surgery, stimulation adjustments, or medication changes within 2 weeks prior to enrolment or at any time during the study period.
4. Pregnancy or breastfeeding.
5. Occurrence of any adverse event during the study that meets the predefined withdrawal criteria (see Safety Monitoring); such participants are withdrawn immediately and not re-randomized.

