## Statistical Analysis Plan

- Sample Size – Assuming within-subject SD = 1.5 NRS points, minimally important difference = 1 point,  $\alpha = 0.05$ , power = 0.90, two-sided paired test → 24 completers needed (calculated with G\*Power). To accommodate 15 % attrition, target enrolment = 28.
- Primary Analysis – Paired t-test (or Wilcoxon signed-rank if non-normal) comparing mean NRS pain across days 3–5 between Active and Sham periods. If a period is aborted due to high pain, the last recorded score will be carried forward for the remaining days. Treatment order and carry-over tested via mixed-effects model with fixed effects for treatment, period, and sequence.
- Secondary Outcomes – Similar within-subject comparisons; Bonferroni correction applied.
- Missing Data – Multiple imputation if > 5 % diary fields missing.

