## Safety Monitoring

All adverse events (AEs) occurring between screening and study exit lead to the immediate withdrawal of the participant from the trial. If the AE is judged related to either the DRG stimulation or the sham condition, it is captured in the study database with these mandatory details: (i) AE type and MedDRA term, (ii) date/time of onset, (iii) action taken (e.g., device OFF, medical treatment), and (iv) final outcome/resolution.

The event report is recorded in Patientkollen within 24 h via the SAE portal and automatically forwarded to the Data Safety Monitoring Board (DSMB) for review at its next meeting.

**Intraperiod stopping rule:** If any diary entry records (i) an NRS pain score > 8 or (ii) an increase  $\geq 4$  points versus Baseline Day 0, the current treatment period is halted. The

participant immediately enters the 24 h wash-out and then crosses to the alternate arm. The episode is logged as an AE (device insufficient efficacy) and triggers a real-time alert to the DSMB.

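### Make the period-adjusted contrast primary, and define what a stopped period measures before its last pain score is carried forward

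*Combined protocol and SAP*

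**What the plan says.** **Primary test.** The Statistical Analysis Plan compares mean NRS on days 3–5 between Active and Sham by a paired t-test, or a Wilcoxon signed-rank test if the data are non-normal. Period appears only in a supporting model: "Treatment order and carry-over tested via mixed-effects model with fixed effects for treatment, period, and sequence". That model's treatment contrast is not made primary.

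**Stopped periods.** The same section says: "If a period is aborted due to high pain, the last recorded score will be carried forward for the remaining days". The stopping rule in Safety Monitoring begins "If any diary entry records (i) an NRS pain score > 8", or shows a rise of at least 4 points from Day 0, and then halts the period. No section says what the outcome of a stopped period is meant to represent.

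**What happens next.** The stopped "participant immediately enters the 24 h wash-out and then crosses to the alternate arm". However, "The episode is logged as an AE (device insufficient efficacy)", and the same section opens with "All adverse events (AEs) occurring between screening and study exit lead to the immediate withdrawal of the participant from the trial". Exclusion Criteria item 5 refers to "Occurrence of any adverse event during the study that meets the predefined withdrawal criteria (see Safety Monitoring)", so it defers to Safety Monitoring and does not settle the matter.

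**Window.** Outcome Measures averages pain over five treatment days; the Statistical Analysis Plan uses days 3–5.

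**The concern.** In a two-period crossover the order is randomised so that period can be separated from treatment. The paired test leaves any period effect in the error term. The schedule gives some reason to expect one: Period 1 starts 24 h after usual therapy is switched off, and Period 2 about six days after. A benefit of usual therapy that outlasts 24 h would appear as a period effect.

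Carry-forward raises a different problem. The score carried is selected for being extreme, and it is then reported as average pain on days 3–5. Starting the window on day 3 keeps days 1–2 out of the average, but carry-forward brings a day 1–2 score back in and repeats it. If stops are more common on sham, the reported difference mixes pain level with stopping.

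Randomisation & Blinding Procedures has the scripts run automatically after data lock, so these choices have to be fixed beforehand.

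**Working it through.** **1. The plan's own figure.** Inputs from the Statistical Analysis Plan: SD 1.5, difference 1, two-sided α 0.05, power 0.90. n = ((1.960 + 1.282) × 1.5 / 1)² = 23.64, so 24, as stated. This works only if 1.5 is the SD of the paired difference. By the noncentral t, power at 24 is 0.878.

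**2. Cost of the period term.** With complete pairs, the adjusted contrast is half the difference between sequences in mean within-participant period difference. Its standard error is (1.5/2) × √(1/n₁ + 1/n₂), with n − 2 degrees of freedom.
- 12:12: standard error 0.306, power 0.877
- 13:11: power 0.875
- 14:10: standard error 0.311, power 0.868

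**3. Gain from the period term.** Assume a within-participant shift π between periods (the documents give none). At 12:12 the paired test's variance is about 1.5² + π² × 24/23, so its SD is 1.58 for π = 0.5 and 1.81 for π = 1. Simulated paired power is 0.85 and 0.77, against 0.88 adjusted. With unequal completers the paired estimate moves by π × (n₁ − n₂)/n. For π = 0.5 this is 0.5 × 2/24 = 0.04 at 13:11 and 0.5 × 4/24 = 0.08 at 14:10. If 4 of 28 (14:14) are lost at random, 8281 of 20475 ways give 12:12 (40 %), 10192 give 13:11 (50 %) and 2002 give 14:10 (10 %).

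**4. Weight of the carried score.** Two diaries a day give six entries on days 3–5. A stop on day 1 or 2 makes all six equal to one entry. A stop at the morning entry of day 4 gives that entry 4/6 of the weight.

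**5. Effect of carry-forward.** Simulation, all inputs assumed: 28 participants; low/mid/high settings with Day 0 mean 2.5/3.0/3.5, diary-noise SD 0.6/0.9/1.2 and participant SD 1.0/1.2/1.5; integer scores; the stopping rule applied to each of ten entries per period. Participant-by-period variance is 1.125 minus noise variance/6, so the SD of the paired difference is about √(2 × 1.125) = 1.5 (1.45 after rounding and bounding). With 2000 trials per cell, the error is about 0.01 on estimates.

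| Sham course relative to active | Full data | Carry-forward | Mixed model |
|---|---|---|---|
| Flat +1 | 0.98/0.97/0.96 | 1.05/1.14/1.23 | 0.99/0.99/1.00 |
| Moderate rise, 0.25 per day | 0.98/0.98/0.95 | 0.99/1.02/1.00 | 0.98/0.99/0.96 |
| Strong rise, 0.75 per day | 2.98/2.95/2.90 | 2.87/2.85/2.72 | 2.99/3.00/3.00 |
| Rebound +2/+1 on days 1/2, then 0 | 0 (true) | 0.48/0.74/0.96 | 0.00–0.13 over all rebound sizes |

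- Flat: sham stops in 11/23/39 % of periods. Carry-forward adds 0.07/0.17/0.27, its SD is 1.61/1.82/2.07, and power is 0.91/0.89/0.86 against 0.92/0.91/0.92 on full data.
- Moderate rise: little bias, but power is 0.90/0.85/0.74 against 0.93/0.92/0.90 on full data.
- Same course in both periods: bias at most 0.01, rejection 4–5 %.
- Sham-only rebound, rejection with carry-forward: +1/+0.5 gives 6/6/11 %, +2/+1 gives 19/36/49 % (52 % in a repeat run at the high setting), +3/+2 gives 84/94/97 %. The mixed model rejects in 4–7 %.

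**6. If withdrawal is literal.** In the flat and moderate-rise runs, dropping everyone stopped gives 0.74–0.85 (power 0.53–0.84). Dropping only those stopped in Period 1 gives 0.93–1.12 (power 0.68–0.88). The unresolved rule therefore matters as much as the scoring.

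**The case against.** **The paired test is valid as planned.** With 1:1 sequences this stands: bias needs unequal completers, and power is lost only if a period effect exists. The planned model already yields the adjusted estimate, so the change is one of rank. It is also almost free.

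**The rebound scenario is chosen.** This largely stands. The device is off for 24 h before both periods, so a rebound may precede either arm. If both arms share +2/+1 there is no bias. If active has half of it, carry-forward still gives 0.38–0.64 (14–23 % rejection). In the sham-only +2/+1 case, 20–41 % of sham periods stop against 2–19 % of active. That is a real early difference, and null only for days 3–5. The scenario shows what can happen, not what will.

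**Carry-forward may be a deliberate failure score.** Possible, but the plan does not say so.

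Four stronger readings are tempting, and the documents do not support them:
- A reader might infer that the automated comparison of labels A and B is itself a period-adjusted contrast. Randomisation & Blinding Procedures does not say what quantity is compared.
- A reader might infer that carry-forward ranks failures inconsistently because a stopped participant can show a smaller rise than an unstopped one. That does not compare two stops, and the analysis uses absolute NRS, not change.
- A reader might see a clash with "Multiple imputation if > 5 % diary fields missing". While carry-forward applies, post-stop entries are naturally read as filled. The question arises mainly if carry-forward is dropped.
- A reader might infer that a mixed model is simply better. It relies on missing-at-random and extrapolates for stops on days 1–2 (35–66 % of stops in the flat and moderate-rise runs, 75–98 % in the rebound runs). Under flat pain it adds only 0.01–0.02 power. Misspecified at the mid setting with the +3/+2 rebound, it rejected falsely in 23 % (linear day); ignoring an autocorrelation of 0.6 gave 11 %.

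**Conclusion.** Both parts hold and should be settled before the scripts are fixed. Neither makes the design unsound.

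The period term is a low-cost safeguard against an effect that the schedule makes plausible but the documents do not show.

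The stopped-period rule is the larger matter: one selected entry can become the whole primary outcome, with no stated estimand. Its direction is not fixed. Relative to pain had the period continued, it overstates the difference under a flat course, is near neutral under a moderate rise and understates under a strong one. It does not inflate type I error in general, but it can when early worsening is confined to, or greater on, sham. These sizes rest on assumed pain courses and variances, so confidence in them is medium. The omission of period, the carried trigger entry and the contradiction over withdrawal are plain in the text.

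**What to change.** 1. **Reconcile first.** Bring the Safety Monitoring statements on withdrawal and crossing over into agreement with each other and with Exclusion Criteria item 5, and say how stopped participants enter the analysis. This decides whether a stopped participant has a pair. Confirm one primary window.
2. **Period.** Make the treatment contrast from the model with treatment, period and sequence primary, and keep the unadjusted paired t-test or Wilcoxon test as sensitivity. Do not use the sequence or carry-over test as a gate, because in a two-period design sequence is confounded with carry-over. Cost: wording, script and one degree of freedom.
3. **Estimand.** State whether a stopped period measures pain had it continued or treatment failure. Do not report a carried-forward trigger score as mean pain on days 3–5 without saying so.
4. **Observed-score analysis.** At minimum, pre-specify a mixed model on observed on-treatment scores with categorical day and treatment-by-day beside carry-forward, including its correlation structure and degrees-of-freedom method. Which analysis is primary follows from the estimand and is the sponsor's choice. Cost: more specification, and reliance on missing-at-random.
5. **If carry-forward is dropped,** name the single rule that handles post-stop entries.

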## Outcome Measures

Category	Measure	Time-Points
Primary	Average NRS pain (0–10) across 5 treatment days	Daily AM & PM
Secondary	Sleep quality (5-point PGIC)*	Daily AM
	Mood (5-point PGIC)*	Daily PM
	Daily activity (5-point PGIC)*	Daily PM
	Adverse events	Continuous
Exploratory	Device usage logs, rescue medication use	Daily

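### The Bonferroni family for the secondary outcomes is not defined, and Holm's procedure over sleep, mood and activity would be a cheap improvement

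*Combined protocol and SAP*

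**What the plan says.** The Statistical Analysis Plan deals with the secondary outcomes in one line: "Similar within-subject comparisons; Bonferroni correction applied". It does not state how many tests are counted, what alpha is divided, or whether the secondary tests depend on the primary result. The only alpha in the section is the 0.05 of the sample-size bullet, given there for a "two-sided paired test".

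The Outcome Measures table puts four rows in its secondary block: sleep quality, mood and daily activity, each on a 5-point scale, and then "Adverse events", collected continuously.

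Objectives & Hypotheses treats these differently. Sleep, mood and activity are to be compared between conditions, safety and tolerability are to be assessed, and carry-over is to be explored.

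**The concern.** A Bonferroni correction is defined only once its family is. Here the table supports four members and the objectives support three. A p-value between 0.0125 and 0.0167 for sleep, mood or activity would be significant under one count and not under the other. Randomisation & Blinding Procedures says that predefined scripts run automatically before the treatment labels are revealed, so someone must code the divisor in advance and the plan does not tell them which.

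The second issue is efficiency. Plain Bonferroni is valid but is uniformly dominated, as a testing procedure, by Holm's step-down on the same family. With about 24 completers, power for the secondary outcomes is limited, and a free gain in rejections is worth taking.

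**Working it through.** **Inputs from the documents.** Alpha 0.05 two-sided; "Assuming within-subject SD = 1.5 NRS points"; "minimally important difference = 1 point"; "24 completers needed". For enrolment the plan states: "To accommodate 15 % attrition, target enrolment = 28".

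**Inputs assumed, because the documents give none.**
- The alpha that Bonferroni divides is 0.05.
- The standardised effect (mean paired difference divided by its SD) for each secondary outcome is 0.5 to 0.667. The upper value borrows the primary's 1/1.5 = 0.667.
- The correlation between outcomes is 0.5, with 0 as a check.
- Paired differences are normal, which is an approximation for 5-point scales.

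**The plan's own figure.** n = (SD × (z₀.₉₇₅ + z₀.₉₀) / δ)² = (1.5 × (1.960 + 1.282) / 1)² = 23.64, rounded up to 24. This takes 1.5 as the SD of the paired difference. An exact paired t calculation gives 26, with power 0.878 at 24; that is a separate matter. With 28 enrolled and 15 % lost, 28 × 0.85 = 23.8, so n = 24 is the right size for what follows.

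**Thresholds.**
- Bonferroni, 4 tests: 0.05/4 = 0.0125.
- Bonferroni, 3 tests: 0.05/3 = 0.0167.
- Holm, 3 tests, from smallest to largest p-value: 0.05/3 = 0.0167, 0.05/2 = 0.025, 0.05/1 = 0.05, stopping at the first failure.

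**Why Holm never rejects less.** Its first threshold equals Bonferroni's and the later ones are larger, so every p-value at or below 0.0167 is still rejected. For error control, suppose m₀ of the three null hypotheses are true. When the first true null comes up for rejection, at most 3 − m₀ others have been rejected, so its threshold is at most 0.05/m₀. The chance that any of the m₀ true nulls has a p-value that small is at most m₀ × 0.05/m₀ = 0.05. No independence is needed.

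**Cost of counting a fourth test** (noncentral paired t, n = 24, power per outcome):

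| Effect | alpha 0.0167 | alpha 0.0125 | Loss |
|---|---|---|---|
| 0.3 | 0.155 | 0.130 | 2.5 points |
| 0.5 | 0.461 | 0.416 | 4.5 points |
| 0.667 | 0.747 | 0.707 | 4.0 points |

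**Holm against Bonferroni** (40,000 simulated trials, n = 24, correlation 0.5, all three effects real):

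| Effect | Measure | Bonferroni/4 | Bonferroni/3 | Holm/3 |
|---|---|---|---|---|
| 0.5 | per outcome | 0.41 | 0.46 | 0.54 |
| 0.5 | all three shown | 0.17 | 0.21 | 0.37 |
| 0.667 | per outcome | 0.71 | 0.75 | 0.83 |
| 0.667 | all three shown | 0.47 | 0.53 | 0.72 |

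Holm's own gain over Bonferroni/3 is 0.54 − 0.46 = 0.08 and 0.83 − 0.75 = 0.08 per outcome. At correlation 0 the power to show all three moves from 0.10 to 0.25 (effect 0.5) and from 0.42 to 0.67 (effect 0.667).

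**When fewer effects are real** (effect 0.5, correlation 0.5, power per real outcome): with two real, Bonferroni/3 gives about 0.465 and Holm 0.496, a gain of 3 points. With one real, the figures are 0.463 and 0.464, no gain.

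**Familywise error over the three outcomes.** With no real effect, Bonferroni/3 and Holm/3 are identical: 0.050 at correlation 0 and 0.044 at 0.5. With one real effect at correlation 0.5 they are 0.033 and 0.040; with two, 0.017 and 0.032. Holm uses more of the permitted 0.05 but stays within it.

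**The case against.** The strongest reply is that Bonferroni is valid, prespecified and conservative, so choosing it is not an error. That stands: Holm is offered as an improvement, not as a correction of an invalid method. It also stands that the power gain depends on assumptions. The effects and the correlation are not in the documents, the case with all three effects real is the most favourable, and the gain vanishes if only one outcome responds.

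The reply on the family is also fair. The objectives separate comparing from assessing, and paired tests like the primary's suit adverse events poorly. They are collected continuously, and Safety Monitoring says that every adverse event ends participation, so a within-subject comparison is hardly feasible. (That section also logs a halted period as an adverse event while the participant crosses over; the two rules must be reconciled, but that is a separate point.) The authors may well have meant three tests. If so, the 4 to 5 points from dropping a fourth test are no gain, but the plan still needs to say so.

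A reader might go further and infer that the plan holds harms to p < 0.0125 and so penalises safety signals. The documents do not support this. No section states four tests or any p-value for adverse events. Safety Monitoring handles harms through withdrawal, recording and review or alerts to the data safety monitoring board, none of which depends on a significance threshold.

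Nor is the change without any downside. Bonferroni has simple simultaneous confidence intervals that match its tests; Holm does not.

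**Conclusion.** The point holds as a gap in specification and a cheap improvement. The secondary family is undefined, so the threshold could be coded as 0.0167 or 0.0125. Replacing Bonferroni by Holm over sleep, mood and activity loses no rejections on that family and keeps its familywise error at 0.05 whatever the correlation; this does not rest on the simulation.

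The size of the gain does rest on assumptions. With 24 completers, correlation 0.5 and effects of 0.5 to 0.667, it is about 8 points per outcome if all three effects are real, which lifts the chance of showing all three from 21 % to 37 % or from 53 % to 72 %. At effect 0.5 it falls to about 3 points with two real effects and about 0 with one.

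The error control covers the three patient-reported outcomes only. Without gating on the primary, error across the primary and the secondary family could reach 0.05 + 0.05 = 0.10 under either method. The conclusion does not extend to a claim that harms are penalised or that a threshold has been set for them.

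**What to change.** Replace the secondary-outcome line in the Statistical Analysis Plan with:

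> Sleep, mood and activity form one family tested with Holm's procedure at two-sided 0.05. Adverse events are summarised descriptively by condition, outside this family and without multiplicity correction.

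Report unadjusted 95 % confidence intervals for the three outcomes and label them as unadjusted. It would also help to state whether the family is tested only after a significant primary result.

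The cost is one short passage in the plan and one line in the analysis script, made before the scripts are fixed. No extra data or participants are needed. What is given up is the simple set of simultaneous intervals that goes with Bonferroni. If the sponsor values those more, Bonferroni with a stated divisor of 3 (0.0167) also closes the gap in specification, at the lower power shown above.

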## Safety Monitoring

All adverse events (AEs) occurring between screening and study exit lead to the immediate withdrawal of the participant from the trial. If the AE is judged related to either the DRG stimulation or the sham condition, it is captured in the study database with these mandatory details: (i) AE type and MedDRA term, (ii) date/time of onset, (iii) action taken (e.g., device OFF, medical treatment), and (iv) final outcome/resolution.

The event report is recorded in Patientkollen within 24 h via the SAE portal and automatically forwarded to the Data Safety Monitoring Board (DSMB) for review at its next meeting.

**Intraperiod stopping rule:** If any diary entry records (i) an NRS pain score > 8 or (ii) an increase  $\geq 4$  points versus Baseline Day 0, the current treatment period is halted. The

participant immediately enters the 24 h wash-out and then crosses to the alternate arm. The episode is logged as an AE (device insufficient efficacy) and triggers a real-time alert to the DSMB.

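### A high-pain diary stop counts both as a mandatory withdrawal and as a crossover, so the plan does not settle whether a Period 1 stop yields a pair for the primary test

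*Combined protocol and SAP*

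**What the plan says.** Safety Monitoring opens with an unconditional rule: "All adverse events (AEs) occurring between screening and study exit lead to the immediate withdrawal of the participant from the trial".

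The intraperiod stopping rule in the same section halts a period on a diary trigger: "If any diary entry records (i) an NRS pain score > 8 or (ii) an increase" of 4 points or more over Day 0. The "participant immediately enters the 24 h wash-out and then crosses to the alternate arm". The rule then adds: "The episode is logged as an AE (device insufficient efficacy) and triggers a real-time alert to the DSMB".

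Two other places bear on the same event:

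- Statistical Analysis Plan, Primary Analysis: "If a period is aborted due to high pain, the last recorded score will be carried forward for the remaining days".
- Exclusion Criteria, criterion 5: "Occurrence of any adverse event during the study that meets the predefined withdrawal criteria (see Safety Monitoring); such participants are withdrawn immediately".

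The primary test is a paired t-test (or Wilcoxon signed-rank) on mean NRS over days 3–5, so each participant needs both periods. On missing data the plan says only "Multiple imputation if > 5 % diary fields missing". On sample size, 24 completers are needed, and "To accommodate 15 % attrition, target enrolment = 28".

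**The concern.** A high-pain stop is by definition an AE. Under the opening sentence the participant leaves the trial; under the stopping rule the participant goes on to the other arm. Both instructions are mandatory and neither refers to the other. Criterion 5 points to withdrawal criteria in Safety Monitoring, but the only AE criterion there is that every AE counts. The stopping rule also gives no disposition for a stop in Period 2, when no other arm is left.

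The choice decides who contributes to the primary test. A participant withdrawn after a Period 1 stop has no Period 2 scores. One who crosses over has a complete pair, with the stopped period scored by carry-forward. Under Interventions, Sham is the stimulator switched off; under Inclusion Criteria, participants have had at least 50 % relief for at least 3 months. Stops should therefore fall more often under Sham, and in those who gain most from stimulation. The loss would not be random, and it would draw on an allowance of only 28 − 24 = 4 participants.

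**Working it through.** **1. The plan's own figure.** Inputs from the Statistical Analysis Plan: SD 1.5, difference 1, two-sided α 0.05, power 0.90. Normal approximation: n = ((1.960 + 1.282) × 1.5 / 1)² = 23.64, so 24, as stated. The exact paired t-test gives 26; at 24 pairs its power is 0.878. Enrolment: 24 × 1.15 = 27.6, so 28.

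**2. Lost pairs alone.** Exact paired-t power with difference and SD held at the plan's values:

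| Pairs lost from 24 | 0 | 2 | 4 | 6 | 8 |
|---|---|---|---|---|---|
| Power | 0.878 | 0.846 | 0.807 | 0.760 | 0.703 |

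**3. How many stops?** The documents give neither a stop rate nor diary variability, so this step rests on assumptions. Simulated trials had 28 participants (14 per sequence), no other dropout, 10 rounded diary entries per period limited to 0–10, between-person SD 1.8, true difference 1, and SD of differences 1.5. The stop was an entry above 8 or at least 4 above one Day 0 entry. Active mean / entry SD was 2/0.5, 3/0.75 or 4/1.0. Day 0 pain was set three ways: (A) at the Active level; (B) varying, like Active and Sham, independently around a personal mean; (C) at the Sham level, meaning recorded with the device off.

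Expected Period 1 stops = 14 × (rate under Sham + rate under Active). Example, A with 4/1.0: 14 × (0.375 + 0.101) = 6.7.

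| Day 0, scenario | Stops Sham / Active, % | Pairs lost | Difference: no stopping | Withdraw Period 1 stops | Cross over and retain | Power: withdraw / retain |
|---|---|---|---|---|---|---|
| A, 2/0.5 | 13.5 / 0.1 | 1.9 | 0.98 | 0.87 | 1.06 | 0.89 / 0.96 |
| A, 3/0.75 | 23.4 / 1.4 | 3.5 | 0.99 | 0.89 | 1.17 | 0.81 / 0.96 |
| A, 4/1.0 | 37.5 / 10.1 | 6.7 | 0.98 | 0.93 | 1.23 | 0.67 / 0.92 |
| B, 2/0.5 | 11.6 / 3.3 | 2.1 | 0.88 | 0.85 | 0.93 | 0.85 / 0.89 |
| B, 3/0.75 | 22.6 / 8.6 | 4.4 | 0.94 | 0.95 | 1.05 | 0.82 / 0.89 |
| B, 4/1.0 | 38.1 / 18.9 | 8.0 | 0.97 | 1.07 | 1.15 | 0.74 / 0.87 |
| C, 2/0.5 | 2 / – | 0.4 | – | – | – | 0.95 / 0.95 |
| C, 3/0.75 | 8 / – | 1.5 | – | – | – | 0.91 / 0.92 |
| C, 4/1.0 | 23 / – | 4.7 | – | – | – | 0.81 / 0.87 |

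Both handling columns use the plan's carry-forward: for Period 2 stops under withdrawal, for all stops under retention. A dash means not tabulated.

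**4. Bias.** Against no stopping, withdrawal shifts the difference by 0.87 − 0.98 = −0.11 at one end (A, 2/0.5) and 1.07 − 0.97 = +0.10 at the other (B, 4/1.0). Retention shifts it by 0.93 − 0.88 = +0.05 to 1.23 − 0.98 = +0.25. The loss of Period 1 stops taken alone lowers the difference by 0.05–0.24 under A and B and by 0.02–0.06 under C. Carry-forward of the remaining Period 2 stops pushes it up again.

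**5. The imputation trigger.** Each participant has 2 × 10 = 20 pain entries; 28 × 20 = 560 in all. A Period 1 withdrawal loses 10 to 19. Read across the trial, one withdrawal is 1.8–3.4 % missing, two are 3.6–6.8 %, and three are 5.4–10.2 %. Read per participant, one withdrawal is 50–95 %. The plan does not say which reading applies, or whether withdrawn participants are imputed.

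**The case against.** The strongest reply is that the documents largely show which rule is meant. The stopping rule is the more specific text, the carry-forward sentence scores exactly this case, and criterion 5 implies that only some AEs lead to withdrawal. Only one sentence points the other way. That is right about intent, and it makes this a drafting conflict and not a flaw in the design. It does not remove the conflict. The all-AE sentence has no exception, staff must act on it as events occur, and the analysis scripts run automatically on the locked data, so the handling has to be settled beforehand.

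The reply on size stands in large part. Literal withdrawal combined with the plan's carry-forward leaves little net bias. In 5 of the 6 scenarios under A and B, retention is further from the no-stopping value than withdrawal is, so part of its power advantage comes from an inflated estimate. Study Schedule & Assessments starts a device-off wash-out on Day 0, so the reference score may well be an off-state score; two of the three scenarios under C then show almost no gap.

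A reader might also infer that imputation could not rescue a single withdrawal. That holds only if the 5 % trigger is read trial-wide, and the plan does not say so.

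**Conclusion.** The contradiction is real and should be corrected before the first enrolment. If the all-AE sentence is followed, every Period 1 high-pain stop costs an observed pair, and those stops are likely to be commoner under Sham. The direction is sound; the size cannot be derived from the documents. Under the assumptions above, 0.4 to 8.0 pairs are lost on average against an allowance of 4. The power gap between the two rules is 0.04 to 0.25 under A and B (0.89 − 0.85; 0.92 − 0.67) and 0.00 to 0.06 under C. None of these figures includes imputation.

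Three stronger readings are not supported:

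- **The plan biases the result toward no effect.** That describes the lost pairs taken alone. With Period 2 stops carried forward, the net shift under A and B is about −0.11 to +0.10.
- **Participants who stop in Period 2 would be dropped too.** This would give a difference of 0.39–0.77 and power of 25–79 % under A and B. However, these participants have data in both periods, and no text excludes them.
- **AE withdrawal must be rebuilt around investigator judgement, or the emergency code-disclosure rule changed.** The first is a safety-policy choice that is not needed to cure the conflict. The second rule is not part of this conflict.

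**What to change.** 1. Safety Monitoring, first sentence: except a diary stop under the intraperiod stopping rule from AE withdrawal.
2. Safety Monitoring, stopping rule: state that such a stop is logged as an AE, that the participant crosses over and stays in the primary analysis under the Statistical Analysis Plan's carry-forward rule, and that a stop in Period 2 ends treatment with the data kept.
3. Exclusion Criteria, criterion 5: align with the exception.
4. Statistical Analysis Plan: add a sensitivity analysis that fills the days after a stop with the mean of that period's entries up to the stop.

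The cost is wording in three sections and one extra analysis, with no new visits or measures. Safety protection is kept: the stop still halts the period and alerts the DSMB.

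The downside is that carrying a high score forward overstates the difference, by 0.05–0.25 under A and B and by less with an off-state Day 0. The mean-to-stop analysis reduces this to 0.02–0.10 (for example, 0.90 − 0.88 under B, 2/0.5, and 1.08 − 0.98 under A, 4/1.0). With no true difference, carry-forward held type I error at 5 % in one scenario under B (3/0.75), where Day 0, Active and Sham are exchangeable. In a separate simulation with 24 pairs, entry SD 1.0 and Day 0 at the Active level, rejection was about 6–9 %. That is a further reason to report the sensitivity analysis beside the primary result.
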